5.6.4 Selection of Doses in the Study

Doses of the DAAs to be used in this study have shown significant antiviral activity both as monotherapy and in combination with pegIFN and RBV. Doses comparable to, and higher than, the DAA doses to be administered in this study have been studied in single- and multiple-dose healthy volunteer studies and administered to HCV-infected subjects as monotherapy or in combination with pegIFN and RBV and found to have a good safety profile and well tolerated. Of note, co-administration of ABT-450/r and ABT-267 at the doses planned for use in this study does not clinically significantly impact plasma exposures compared to administration as single agents. Therefore doses selected based on data from monotherapy studies are considered appropriate for use when these agents are combined.

ABT-450/r

The dose of ABT-450/r is 200/100 mg QD. This is higher than the 150 mg dose used in Phase 3 studies and the approved dose of ABT-450 for HCV GT1 infection with the interferon free 3-DAA regimen. The 200 mg dose has been evaluated in Phase 2a study (Study M11-602) with peg-IFN and ribavirin for 12 weeks; in the Phase 2a and 2b Studies M12-998 and M11-652, the 200 mg dose was administered for 12 to 24 weeks with 25 mg ABT-267 with and without ribavirin. Doses higher than 200 mg have been evaluated in Phase 2 Study M12-746 with ABT-333 and ribavirin for 12 weeks as well as

in Phase 1 Study M12-187 and Study M12-221 for up to 14 days with ABT-267. Studies in both healthy volunteers (Study M12-187) and HCV-infected subjects (Study M12-746) suggest that a higher dose of ABT-450/r (250/100 mg QD) may be associated with a risk of elevated ALT levels when co-administered with other DAAs (ABT-333 or ABT-267 + ABT-333). Therefore, the maximum ABT-450 dose administered in this study will not exceed 200 mg daily for 24 weeks.

ABT-267

The 25 mg dose of ABT-267 is the dose evaluated in Phase 3 studies and the approved dose of ABT-267 for HCV GT1 infection with the interferon free 3-DAA regimen. This was the same dose that has been evaluated in multiple Phase 2 studies (Studies M11-652, M12-998, M13-393). The dose of ABT-267 in this study is 25 mg QD. Following 3 days of ABT-267 monotherapy at doses of 1.5 mg, 5 mg QD, 25 mg QD, 50 mg QD and 200 mg QD, in Study M12 116 and Study M13-386, mean viral load decreases were 2 to 3 log₁₀ IU/mL and comparable across doses. In addition, data from Phase 2a study of ABT-267 with pegIFN and RBV (Study M12-114) suggest that the 3 doses used in that study (5 mg QD, 50 mg QD and 200 mg QD) are all well tolerated and show comparable short term antiviral activity. Resistance analysis from a short-term monotherapy trial (Study M12-116) suggests that ABT-267 doses greater than 25 mg QD do not appear to confer an advantage in suppression of commonly selected resistant variants. The maximum ABT-267 dose administered in this study will not exceed 25 mg daily for 24 weeks.

RBV

The daily dose of RBV in this study is 1,000 mg to 1,200 mg, divided twice daily. This dose is approved for treatment of adult patients with chronic hepatitis C in combination with pegIFN. This dose is selected for this study because the safety profile has been well characterized when administered with pegIFN, including the incidence of hemolytic anemia, and there are well-defined dose reduction criteria in the event of RBV-induced anemia.

pegIFN

PegIFN will be dosed per the package insert in this study.¹¹ PegIFN will be dosed at 180 µg/0.5 mL SC once a week for the duration of 48 weeks. This dose is approved for treatment of adult patients with chronic hepatitis C in combination with RBV. The same dose is selected for this study because the safety profile has been well characterized when administered with RBV, and there are well-defined dose reduction criteria in the event of hematologic adverse effects.

6.0 Adverse Events

The investigator will monitor each subject for clinical and laboratory evidence of adverse events on a routine basis throughout the study. The investigator will assess and record any adverse event in detail including the date of onset, event diagnosis (if known) or sign/symptom, severity, time course, duration and outcome, relationship of the adverse event to study drug, and any action(s) taken. For serious adverse events not considered "probably related" to study drug, the investigator will provide an Other cause of the event. For adverse events to be considered intermittent, the events must be of similar nature and severity. Adverse events, whether in response to a query, observed by site personnel, or reported spontaneously by the subject will be recorded.

All adverse events will be followed to a satisfactory conclusion.

6.1 Definitions

6.1.1 Adverse Event

An adverse event (AE) is defined as any untoward medical occurrence in a patient or clinical investigation subject administered a pharmaceutical product and which does not necessarily have a causal relationship with this treatment. An adverse event can therefore be any unfavorable and unintended sign (including an abnormal laboratory finding), symptom, or disease temporally associated with the use of a medicinal (investigational) product, whether or not the event is considered causally related to the use of the product.

Such an event can result from use of the drug as stipulated in the protocol or labeling, as well as from accidental or intentional overdose, drug abuse, or drug withdrawal. Any worsening of a pre-existing condition or illness is considered an adverse event.

Laboratory abnormalities and changes in vital signs are considered to be adverse events only if they result in discontinuation from the study, necessitate therapeutic medical intervention, (meets protocol specific criteria [see Section 6.7 regarding toxicity management]) and/or if the investigator considers them to be adverse events.

An elective surgery/procedure scheduled to occur during a study will not be considered an adverse event if the surgery/procedure is being performed for a pre-existing condition and the surgery/procedure has been pre-planned prior to study entry. However, if the pre-existing condition deteriorates unexpectedly during the study (e.g., surgery performed earlier than planned), then the deterioration of the condition for which the elective surgery/procedure is being done will be considered an adverse event.

6.1.2 Serious Adverse Events

If an adverse event meets any of the following criteria, it is to be reported to AbbVie as a serious adverse event (SAE) within 24 hours of the site being made aware of the serious adverse event.

| | |
|---|--|
| Death of Subject | An event that results in the death of a subject. |
| Life-Threatening | An event that, in the opinion of the investigator, would have resulted in immediate fatality if medical intervention had not been taken. This does not include an event that would have been fatal if it had occurred in a more severe form. |
| Hospitalization or Prolongation of Hospitalization | An event that results in an admission to the hospital for any length of time or prolongs the subject's hospital stay. This does not include an emergency room visit or admission to an outpatient facility. |
| Congenital Anomaly | An anomaly detected at or after birth, or any anomaly that results in fetal loss. |

| | |
|--|--|
| Persistent or Significant Disability/Incapacity | An event that results in a condition that substantially interferes with the activities of daily living of a study subject. Disability is not intended to include experiences of relatively minor medical significance such as headache, nausea, vomiting, diarrhea, influenza, and accidental trauma (e.g., sprained ankle). |
| Important Medical Event Requiring Medical or Surgical Intervention to Prevent Serious Outcome | An important medical event that may not be immediately life-threatening or result in death or hospitalization, but based on medical judgment may jeopardize the subject and may require medical or surgical intervention to prevent any of the outcomes listed above (i.e., death of subject, life-threatening, hospitalization, prolongation of hospitalization, congenital anomaly, or persistent or significant disability/incapacity). Additionally, any elective or spontaneous abortion or stillbirth is considered an important medical event. Examples of such events include allergic bronchospasm requiring intensive treatment in an emergency room or at home, blood dyscrasias or convulsions that do not result in inpatient hospitalization, or the development of drug dependency or drug abuse. |

For serious adverse events with the outcome of death, the date and cause of death will be recorded on the appropriate case report form.

6.2 Adverse Event Severity

The investigator will use the following definitions to rate the severity of each adverse event:

| | |
|-----------------|---|
| Mild | The adverse event is transient and easily tolerated by the subject. |
| Moderate | The adverse event causes the subject discomfort and interrupts the subject's usual activities. |
| Severe | The adverse event causes considerable interference with the subject's usual activities and may be incapacitating or life-threatening. |

6.3 Relationship to Study Drug

The investigator will use the following definitions to assess the relationship of the adverse event to the use of DAA (ABT-450/r or ABT-267), RBV and pegIFN:

| | |
|-----------------------------|--|
| Probably Related | An adverse event has a strong temporal relationship to study drug or recurs on re-challenge and an Other cause of event is unlikely or significantly less likely. |
| Possibly Related | An adverse event has a strong temporal relationship to the study drug and an Other cause of event is equally or less likely compared to the potential relationship to study drug. |
| Probably Not Related | An adverse event has little or no temporal relationship to the study drug and/or a more likely Other cause of event exists. |
| Not Related | An adverse event is due to an underlying or concurrent illness or effect of another drug and is not related to the study drug (e.g., has no temporal relationship to study drug or has a much more likely Other cause of event). |

For causality assessments, events meeting the categories of probably or possibly will be considered "associated." Events that are probably not or not related will be considered "not associated." In addition, when the investigator has not reported a causality or deemed it not assessable, AbbVie will consider the event associated.

[figure not shown]
If an investigator's opinion of possibly, probably not, or not related to study drug is given, an Other cause of event must be provided by the investigator for the serious adverse event.

6.4 Adverse Event Collection Period

All adverse events reported from the time of study drug administration until 30 days following discontinuation of study drug administration (including pegIFN and RBV) have elapsed will be collected, whether solicited or spontaneously reported by the subject. In addition, serious adverse events will be collected from the time the subject signed the study-specific informed consent through the end of Substudy 3 (End of Study).

Adverse event information will be collected as shown in [Figure 4](#).

Figure 4. Adverse Event Collection

6.5 Adverse Event Reporting

In the event of a serious adverse event, whether associated with study drug or not, the investigator will notify Clinical Pharmacovigilance within 24 hours of the site being made aware of the serious adverse event by entering the serious adverse event data into the EDC system. Serious adverse events that occur prior to the site having access to the RAVE[®] system or if RAVE is not operable should use the SAE non-CRF paper forms and send them to Clinical Pharmacovigilance within 24 hours of the site being aware of the serious adverse event.

For safety concerns, contact the Antiviral Safety Team at:

For any subject safety concerns, please contact the physician listed below:

In emergency situations involving study subjects when the primary Study Designated Physician (SDP) is not available by phone, please contact the 24-hour AbbVie Medical Escalation Hotline where your call will be re-directed to a designated AbbVie SDP.

AbbVie will be responsible for Suspected Unexpected Serious Adverse Reactions (SUSAR) reporting for the Investigational Medicinal Product (IMP) in accordance with Directive 2001/20/EC. The reference document used for SUSAR reporting in the EU countries will be the most current version of the Investigator's Brochure.

6.6 Pregnancy

Subjects and their partners should avoid pregnancy and males should avoid sperm donation throughout the course of the study, starting with Study Day 1 and for 7 months (or per local RBV label) after the last dose of RBV.

Pregnancy in a study subject must be reported to AbbVie within 1 working day of the site becoming aware of the pregnancy. Subjects who report a positive pregnancy test during

the Treatment Period must be notified to stop RBV immediately. Administration of DAA's, including ritonavir, and Peginterferon may be continued at the investigator's discretion if the benefit of continuing therapy is felt to outweigh the risk (Section 5.4.1). Subjects will continue to be monitored for antiviral drug resistance in the Post-Treatment Period as described in Section 5.1.4.

Information regarding a pregnancy occurrence in a study subject and the outcome of the pregnancy will be collected for pregnancies occurring up to 7 months (or per local RBV label) after the last dose of RBV. The investigator is encouraged to report the pregnancy information to the voluntary RBV Pregnancy Registry as applicable.

Male subjects who are not surgically sterile must either abstain from sexual intercourse or agree to use a double barrier method of birth control (condom), including informing their partner(s) to use an effective method of birth control (e.g., contraceptive sponge, diaphragm, or vaginal ring with spermicidal jellies or creams) for 7 months (or per local RBV label) after the last dose of RBV. In the event of pregnancy occurring in the partner of an enrolled subject, the investigator should contact the AbbVie Study Designated Physician to discuss the potential benefit of the male subject remaining on study drug treatment. If considered appropriate, the subject may remain in the study and the investigator should counsel the subject on the pregnancy risks associated with RBV, and instruct him to use 2 effective forms of contraception (including at least one barrier method) for the remainder of the partner's pregnancy. The investigator is encouraged to report the partner's pregnancy information to the voluntary RBV Pregnancy Registry.

Pregnancy in a study subject is not considered an adverse event. However, the medical outcome of an elective or spontaneous abortion, stillbirth or congenital anomaly is considered a serious adverse event and must be reported to AbbVie within 24 hours of the site becoming aware of the event.

6.7 Toxicity Management

For the purpose of medical management, all adverse events and laboratory abnormalities that occur during the study must be evaluated by the investigator. A table of Clinical Toxicity Grades for evaluating laboratory abnormalities is provided in [Appendix C](#). This table should be used in determination of the appropriate toxicity management as discussed in Section [6.7.1](#) through Section [6.7.5](#).

A drug-related toxicity is an adverse event or laboratory value outside of the reference range reported as an adverse event that is judged by the investigator or AbbVie to be either "possibly related" or "probably related" to the study drug (Section [6.3](#)). A toxicity is deemed "clinically significant" based on the medical judgment of the investigator. During the study, timeliness of EDC data entry to reflect study drug dose interruptions and/or dose modifications and consequent required adverse events insures that the AbbVie Safety Team (Study Designated Physician, safety monitor) have the data necessary for signal detection at safety data review meetings. The investigator should ensure that any interruptions or modifications and consequent required adverse events are entered into the appropriate eCRFs within 5 business days.

Lowering of the pegIFN and RBV dose for reasons not provided in the protocol is permitted. The following guidelines should be used for study drug-related toxicity management.

6.7.1 Grades 1 or 2 Laboratory Abnormalities and Mild or Moderate Adverse Events

Subjects who develop a study drug-related mild or moderate adverse event or Grade 1 or 2 laboratory abnormality, other than those discussed separately in Section [6.7.3](#), Section [6.7.4](#) and Section [6.7.5](#), may continue study drugs with follow-up per study protocol and in accordance with local standard of care.

6.7.2 Grades 3 or 4 Laboratory Abnormalities and Severe or Serious Adverse Events

If a subject experiences a Grade 3 or greater laboratory abnormality during the study (other than those discussed in Section 6.7.3 and Section 6.7.4 below), the abnormal laboratory test should be repeated. If the Grade 3 or greater abnormality is confirmed, then all study drugs should be interrupted and the subject monitored until the laboratory parameter has returned to its baseline level or stabilized. Study drugs may be resumed only with approval of the AbbVie Study Designated Physician. If the investigator believes that a Grade 3 or greater laboratory parameter is not clinically significant or is not related to study drug and that study drug discontinuation is not warranted, the study drug may be continued with approval of the AbbVie Study Designated Physician.

Study drug-related Grade 3 or higher elevations in uric acid, total cholesterol or triglycerides do not require study drug discontinuation, but study drug may be interrupted if deemed necessary by the investigator.

If a subject experiences a severe adverse event or a serious adverse event and that event is considered possibly or probably related to study drug by the investigator, the AbbVie Study Designated Physician should be notified and all study drugs should be interrupted. The investigator should ensure that the serious adverse event is report to AbbVie Safety within 24 hours of awareness of it; a severe event should be entered into EDC within 5 business days. Dose interruptions (or discontinuations) should be entered into the appropriate eCRFs within 5 business days.

6.7.3 Management of Decreases in Hemoglobin

Reductions in hemoglobin are a well characterized side effect of ribavirin exposure. Hematologic abnormalities which the investigator believes are due to RBV therapy may be managed according to Table 12. Management will be different for subjects without a history of known cardiac disease and subjects with known cardiac disease.

If a subject experiences a hemoglobin decrease (as outlined in [Table 12](#)), a confirmatory test should be performed. If the hemoglobin decrease is confirmed, the management guidelines in [Table 12](#) should be followed.

Use of hematologic growth factors (e.g., epoetin, filgrastim) is permitted at the discretion of the investigator, only with approval of the AbbVie Study Designated Physician (see [Section 5.2.3.2](#) for further details). Management of hematologic growth factor therapy is the responsibility of the Investigator, and growth factors will not be provided by AbbVie.

Alternate management of hemoglobin decreases requires approval of the AbbVie Study Designated Physician.

Alternative management of the RBV dose in the setting of reduced renal function will also require approval of the AbbVie Study Designated Physician.

Table 12. Hematologic Toxicities

| Hemoglobin in Patients with No History of Cardiac Disease | |
|--|---|
| Hemoglobin < 10.0 g/dL, but ≥ 8.5 g/dL | Study drugs may be continued |
| | Reduce RBV dose to 600 mg/day and continue to monitor hemoglobin per protocol |
| | If hemoglobin increases to ≥ 10 g/dL, may increase RBV; with gradual dose increases in 200 mg increments towards original dose If Hb decreases to < 8.5 g/dL see appropriate row below |
| Hemoglobin < 8.5 g/dL | Permanently discontinue all study drugs Manage the subject as medically appropriate |
| | Enter discontinuation into appropriate eCRFs and create corresponding adverse event |
| | |
| Hemoglobin in Patients with History of Stable Cardiac Disease | |
| Hemoglobin decrease of ≥ 2 g/dL during a 4-week treatment period | Study drugs may be continued |
| | Reduce RBV dose to 600 mg/day and continue to monitor hemoglobin levels per protocol; manage subject as medically appropriate; AbbVie Study Designated Physician may be contacted |
| | If a subsequent hemoglobin result is greater than the level that triggered the dose reduction, the investigator may gradually increase RBV in 200 mg increments towards original dose |
| Hemoglobin <12 g/dL despite 4 weeks at reduced dose | Permanently discontinue all study drugs; manage subject as medically appropriate |
| | Enter discontinuation into appropriate eCRFs and create corresponding adverse event (AE) |

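### Table 12 gives subjects with stable cardiac disease no haemoglobin limit that acts on a single confirmed value, so below 8.5 g/dL they can have a weaker instruction than subjects without cardiac disease

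*Protocol*

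**What the plan says.** Section 6.7.3 says that cardiac and non-cardiac subjects are managed differently, and Table 12 has a block for each.

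- **Block headed "Hemoglobin in Patients with No History of Cardiac Disease".** From 8.5 to below 10.0 g/dL, RBV goes to 600 mg/day. Below 8.5 g/dL all study drugs are permanently discontinued. The first row points to the second: "If Hb decreases to < 8.5 g/dL see appropriate row below".
- **Block for stable cardiac disease.** The first row is a "Hemoglobin decrease of ≥ 2 g/dL during a 4-week treatment period": study drugs may go on, RBV goes to 600 mg/day, and contact with the sponsor's physician is optional. The second row is "Hemoglobin <12 g/dL despite 4 weeks at reduced dose": all study drugs are permanently discontinued.

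Section 6.7.3 adds: "Alternate management of hemoglobin decreases requires approval of the AbbVie Study Designated Physician".

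**The concern.** Haemoglobin reduction is a known effect of RBV, and RBV is given for up to 48 weeks. Table 12 is where the protocol puts its on-treatment haemoglobin limits. The cardiac block has no limit that works on the value alone: its first row needs a rate of fall, and its second needs 4 weeks already spent at reduced dose. A very low value that arrives before those 4 weeks have passed, or arrives slowly, therefore gets less from the table in a cardiac subject than in a non-cardiac one. At stake is safety management in the group that section 6.7.3 singles out for separate handling.

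**Working it through.** The plan has no figure to reproduce. The check applies the Table 12 rows to example courses. Starting values are assumptions: exclusion criterion 11 (section 5.2.2) requires haemoglobin not below the lower limit of normal, but that limit is not given.

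**1. Fast fall, 13.0 to 8.2 g/dL in 4 weeks.** The fall is 13.0 − 8.2 = 4.8, which is at least 2, so the cardiac reduction row applies: drugs may go on, RBV 600 mg/day. Since 8.2 < 8.5, the non-cardiac row is a permanent stop. Laboratory tests at TI Weeks 1 and 2 (Table 5) may catch the first 2 g/dL sooner. Even so, a subject reduced at Week 1 has had only 4 − 1 = 3 weeks at reduced dose by Week 4, so the cardiac stop is not yet in force.

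**2. Slow fall, 1.2 g/dL per 4 weeks from 13.0.**

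| Visit | Hb (g/dL) | Fall in 4 weeks | Cardiac row met | Non-cardiac row met |
|---|---|---|---|---|
| Day 1 | 13.0 | – | none | none |
| TI Week 4 | 11.8 | 1.2 | none | none |
| TI Week 8 | 10.6 | 1.2 | none | none |
| TI Week 12 | 9.4 | 1.2 | none | RBV to 600 mg/day |
| TI Week 16 | 8.2 | 1.2 | none | permanent stop |

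**3. Is the slow example tuned?** From 13.0 to 8.5 is 4.5 g/dL, and 48 weeks hold 48 / 4 = 12 four-week periods. The slowest steady rate that reaches 8.5 is 4.5 / 12 = 0.375 g/dL per 4 weeks. So any steady fall from just over 0.375 to just under 2.0 passes below 8.5 within 48 weeks without meeting the cardiac trigger. At 1.9 per 4 weeks, other assumed starts give 12.0 − 2 × 1.9 = 8.2 at Week 8, 14.0 − 3 × 1.9 = 8.3 at Week 12 and 16.0 − 4 × 1.9 = 8.4 at Week 16.

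**4. Where the cardiac block is stricter.** A fall from 13.0 to 11.0 within 4 weeks cuts RBV in a cardiac subject, while a non-cardiac subject has no action until below 10.0. After 4 weeks at reduced dose, the cardiac stop is 12 − 8.5 = 3.5 g/dL higher.

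**5. Does other text supply the missing limit?**

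- Section 6.7.1 lets subjects continue with a "Grade 1 or 2 laboratory abnormality, other than those discussed separately in Section" 6.7.3, 6.7.4 and 6.7.5.
- Section 6.7.2 requires repeat testing and interruption from Grade 3, "other than those discussed in Section 6.7.3 and Section 6.7.4 below". Appendix C puts 8.0 to below 10.0 g/dL in Grade 2, so 8.2 would not reach that rule even without the exclusion.
- Section 5.3.1.1 requires out-of-range values that the investigator considers clinically significant to be repeated and followed to resolution.
- Section 6.7.2 also calls for interruption for a related severe or serious adverse event. Section 6.7 permits other lowering of RBV, and section 5.4.1 lets the investigator discontinue a subject at any time.
- Section 5.5.6 refers to local prescribing information, which is not in the documents.

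None of the last three items states a haemoglobin value in these documents.

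**The case against.** The case on the other side is substantial.

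- **Table 12 is not the only instruction.** Section 5.5.6 sends RBV changes to the local label, section 5.6.4 relies on well-defined dose-reduction criteria for anaemia, and 6.7.3 opens in permissive terms. The label may set a cardiac floor. This stands: the gap is in the table text, and no gap in care is shown.
- **The cardiac block is more cautious in most situations.** It can cut RBV earlier, its reduction row asks for medically appropriate management and mentions the sponsor's physician, and it permits continuation without ordering it. This stands. A reader might infer that cardiac subjects are less protected overall; the documents do not support that.
- **Entry criteria limit cardiac risk.** Inclusion 7 and exclusions 10 and 14 let the investigator keep out unsuitable subjects. This lowers the number affected.
- **The examples are constructed.** A steady fall with no reaction from the investigator is an assumption. They show how the rules act, not how often. It is also arguable that a value below 8.0 g/dL meeting no cardiac row falls back to 6.7.2. That would still leave 8.0 to below 8.5 uncovered.

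A reader might also infer that the cardiac rows contradict each other. The re-escalation line reads "If a subsequent hemoglobin result is greater than the level that triggered the dose reduction, the investigator may gradually increase RBV", and after 4 weeks at reduced dose a result above that level but below 12 g/dL also meets the stop row. This is not a conflict: the stop is mandatory and re-escalation is optional, so stopping complies with both.

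**Conclusion.** The point holds for the table text. Before 4 weeks at reduced dose, or after a slow fall that never meets the trigger, a cardiac subject below 8.5 g/dL has a weaker Table 12 instruction than a non-cardiac subject with the same value. Elsewhere the cardiac rules are often the stricter ones.

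Severity is minor. The number of cardiac subjects is not stated and may be zero of up to 35. In the Phase 3 RBV arms, which had no pegIFN, haemoglobin below 10 g/dL occurred in 5.5% to 11.0% and below 8.0 g/dL in 0.1% to 1.4% (Protocol Table 3). The courses shown rest on assumed starting values and steady falls. No effect on the primary endpoint or any other analysis follows.

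**What to change.** In Table 12, apply the RBV reduction below 10.0 g/dL and the permanent stop below 8.5 g/dL to all subjects, whatever their cardiac history, as a minimum floor in addition to the existing cardiac rows. The sponsor's physicians may prefer a higher floor for cardiac subjects.

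The cost is wording in one table, with no new visits or tests. The downside is possibly a few more RBV reductions or discontinuations in cardiac subjects. One consequence should be intended: a reduction made under the floor would also start the 4 weeks after which the cardiac stop below 12 g/dL applies.
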